14.6 Missing data and sensitivity analyses

Every attempt will be made to collect full follow-up data on all study participants; it is thus anticipated that missing data will be minimal. Participants with missing primary outcome data will not be included in the primary analysis in the first instance (NRS pain score will be considered as missing if fewer than 5 days recorded). This presents a risk of bias, and sensitivity analyses will be undertaken to assess the possible impact of the risk. In brief, this will include a multiple imputation approach.

Further sensitivity analysis will include a per protocol analysis.

Full details will be included in the Statistical Analysis Plan.

14.7 Planned final analyses

The primary analysis for the trial will occur once all participants have completed the 6 month assessment and corresponding outcome data has been entered onto the trial database and validated as being ready for analysis. This analysis will include data items up to and including the 6 month assessment and no further.

15.HEALTH ECONOMICS

A separate Health Economics Analysis Plan will be produced and will provide a more comprehensive description of the planned analyses. A brief outline of these analyses is given below.

15.1 Within-trial economic evaluation

A within-trial health economics analysis will assess the cost-effectiveness of FREMS compared to TENS for patients with PDPN. Initially a cost-consequences analysis will be conducted to describe all important costs and outcomes. Subsequently, a trial-based cost utility analysis from an NHS/personal social services (PSS) perspective will be conducted. The primary outcome for the economic evaluation will be the cost per QALY gained over a 6-month period. The cost-utility analysis will be conducted in line with the NICE Guide to the Methods of Technology Appraisal (2013) [83].

QALYs will be estimated using the EQ-5D-5L questionnaire reported at baseline, month 3 and month 6 and the EQ-5D-5L will be valued using published population tariff values, allowing QALYs to be estimated using the trapezium rule to calculate the area under the curve.

NHS resource use will be measured for each participant over a 6-month period. This will include all medication costs, visits to health services, hospital stays and any social care and community support. Medical costs will be taken from the study medication records, and other NHS resources used will be self-reported by participants. Unnecessary questions in the CSRI will be removed to reduce the burden for participants; however, questions relating to personal costs such as travel costs incurred and time-off-work will be retained for sensitivity analysis. Unit cost data will also be derived from nationally represented sources such as the British National Formulary [84], the National Schedule for Reference Costs [85] and the Unit Costs of Health and Social Care [86]. In order to cost the intervention, the cost of the FREMS machine will be obtained and annuitized given the lifespan of the machine and a discount rate of 3.5%. A cost per patient will then be estimated.

The incremental costs and QALYs of FREMS compared to TENS will be estimated over the 6-month follow-up period and results will be expressed as incremental cost-effectiveness ratios (ICERs). Bootstrapped estimates of the ICERs will be sampled to allow the probability of FREMS being cost-effective to be determined. This will be reported numerically, as well as visually by providing Cost Effectiveness Acceptability Curves (CEACs). Sensitivity analysis will focus on assessing the cost-effectiveness of FREMS from a societal perspective.

15.2 Model-based economic evaluation

In order to assess the long-term cost-effectiveness of FREMS over the lifetime of the patient, a model-based economic evaluation will be conducted. The model will be populated with data (costs, utilities etc.) from various sources, including data obtained from the RCT, literature reviews and expert opinions. A Markov model will be used to estimate the lifetime cost-effectiveness of FREMS. Incremental cost-effectiveness ratios will be estimated and a cost-effectiveness plane as well as a cost-effectiveness acceptability curve constructed. Deterministic and probabilistic sensitivity analysis will be used to assess the robustness of the results obtained from the model.

16.SUBSTUDY

Based on recommendations by the European Medicine Agency for the design of drug trials in chronic neuropathic pain conditions, this trial includes an explorative sub-study to allow stratification according to stimulus evoked pain [49].

Quantitative sensory testing (QST) according to the German Network for Neuropathic pain will assess detection and pain threshold for a variety of sensory qualities [67]. A gain or loss of function can then be determined by calculating z-scores based on values from the normal population. Presence or absence of plasticity changes like central wind-up will also be assessed with the assessment of temporal summation (increased pain to repeated stimuli). We expect to recruit up to 100 patients between Sheffield and Liverpool providing QST data at baseline which can be used to identify a preferential profile for responders to the FREMS treatment [76]. QST will also be able to determine any meaningful recovery or worsening of sensory function 3 months after treatment as a correlate for the safety of the treatment in patients with an underlying neuropathy.

QST is a non-invasive methodology used to assess a patient's somatosensory system function in peripheral neuropathic pain. In this study, QST will be performed following the standardised protocol of the German Research Network on Neuropathic Pain, exploring 11 sensory modalities. It will be performed by the technician trained according to the standards defined by the German Network using equipment already owned by the Trust. The time required for a complete QST is expected to be about

16.1 Sensory testing protocol

A formal standardised QST protocol will be performed according to the German Research Network on Neuropathic Pain protocol. This battery of tests has been extensively validated and has age and gender at birth specific normative ranges. All tests will be performed on a single leg with the same leg used for both baseline and follow up assessments. The testing protocol has the following components:

Thermal Sensations

The tests for thermal sensations will be performed using a TSA 2001-II (MEDOC, Israel) thermal sensory testing device. All thresholds will be obtained with ramped stimuli (1 °C/s) that will be terminated when the subject presses a button. Cut-off temperatures are 0 and 50 °C. The baseline temperature is 32 °C. Cold detection threshold and warm detection threshold will be measured as the threshold temperature able to elicit, respectively, a sensation of cold or warm. Similarly, cold pain threshold, and heat pain threshold will be measured as the threshold temperature able to elicit a painful or distressing cold or warm sensation. For each modality, the mean threshold temperature of three consecutive measurements will be calculated. Later, the thermal sensory limen procedure, consisting of six alternating cold and warm stimuli, will be carried out. The mean temperature span for sensation change and the number of paradoxical heat sensations during the cold stimuli will be recorded.

Mechanical detection threshold (MDT)

This will be measured with a standardised set of modified von Frey hairs (Opti-hair2-Set, Marstock Nervtest, Germany) that exert forces upon bending between 0.25 and 512 mN graded by a factor of 2 (1– 2 s contact time). The contact area of the von Frey hairs with the skin is of uniform size and shape (rounded tip, 0.5 mm in diameter) to avoid sharp edges that would facilitate nociceptor activation. Using the “method of limits”, five threshold determinations will be made, each with a series of ascending and descending stimulus intensities. The final threshold was the geometric mean of these five series.

Mechanical pain threshold (MPT)

This will be measured using custom-made weighted pinprick stimuli as a set of seven pin- prick mechanical stimulators with fixed stimulus intensities (flat contact area of 0.2 mm diameter) that exerts forces of 8, 16, 32, 64, 128, 256, and 512 mN. The stimulators will be applied at a rate of 2 seconds on, 2 seconds off in an ascending order until the first percept of sharpness is reached. The final threshold will be the geometric mean of five series of ascending and descending stimuli. This test is designed to detect pinprick hypoalgesia.

Stimulus/response-functions: mechanical pain sensitivity for pinprick stimuli and dynamic mechanical allodynia

Mechanical pain sensitivity (MPS)

This will be assessed using the same set of seven weighted pinprick stimuli to obtain a stimulus–response function for pinprick-evoked pain. Subjects will be asked to give a pain rating for each stimulus on a ‘0–100’ numerical rating scale (‘0’ indicating “no pain”, and ‘100’ indicating “most intense pain imaginable”). This test is designed to detect pinprick hyperalgesia.

Dynamic mechanical allodynia (DMA)

This will be assessed as part of the test above, using a set of three light tactile stimulators as moving innocuous stimuli: Cotton wisp exerting a force of approximately 3 mN, a cotton wool tip fixed to an elastic strip exerting a force of approximately 100 mN, and a standardised brush (Somedic, Sweden) exerting a force of approximately 200–400 mN. The tactile stimuli will be applied with a single stroke of approximately 2 cm in length over the skin. These stimuli will be inserted into a balanced protocol in between the pinprick stimuli.

A total of 50 stimuli, 15 tactile and 35 pinprick, will be delivered with the subject giving numerical pain ratings for each stimulus. These stimuli will be given in runs of 10, and each run will consist of a different pseudo-random sequence of three tactile and seven pinprick stimuli. All stimuli will be applied with an approximately 10 second inter-stimulus interval – well below the critical frequency for wind-up. Mechanical pain sensitivity will be calculated as the geometric mean of all numerical ratings for pinprick stimuli. Dynamic mechanical allodynia will be calculated as the geometric mean (compound measure) of all numerical ratings across all three different types of light touch stimulators.

Wind-up-ratio (WUR) representing the perceptual correlate of temporal pain summation.

In this test, the perceived intensity of a single pinprick stimulus (128 mN pinprick) will be compared with that of a series of 10 repetitive pinprick stimuli of the same physical intensity (1/s applied within an area of 1 cm²). The subject will be asked to give a pain rating representing the single stimulus, and the estimated mean over the whole series of 10 stimuli using a ‘0–100’ numerical rating scale. The whole procedure will be repeated five times. Wind-up ratio will be calculated as the ratio: mean rating of the five series divided by the mean rating of the five single stimuli. Wind-up is a frequency-dependent increase in excitability of spinal cord neurons that reaches a plateau after about five stimuli, the perceptual correlate of which can be described by this ratio.

Vibration detection threshold (VDT)

This test will be performed with a Rydel–Seiffer graded tuning fork (64 Hz, 8/8 scale) that will be placed over a bony prominence and left there until the subject cannot feel vibration anymore. Vibration detection threshold will be determined as a disappearance threshold with three stimulus repetitions.

Pressure Pain Threshold (PPT)

This will be performed over the calf muscle with a pressure gauge device (FDN100, Wagner Instruments, USA) with a probe area of 1 cm² (probe diameter of 1.1 cm) that exerts forces up to 10 kg/cm² corresponding to approximately 1000 kPa. The pressure pain threshold will be determined with three series of ascending stimulus intensities, each applied as a slowly increasing ramp of 25 kPa/s (approximately 0.5 kg/cm²/s).

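### Section 16.1 defines MPS and DMA as plain geometric means of ratings that may be 0, so one zero among non-zero ratings sets the whole score to 0

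*Protocol*

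**What the plan says.** Section 16.1 of the protocol describes the pinprick and light-touch ratings as one combined test. Each stimulus is rated on a 0–100 scale on which 0 stands for no pain. The number of ratings is fixed: "A total of 50 stimuli, 15 tactile and 35 pinprick, will be delivered with the subject giving numerical pain ratings for each stimulus".

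The scoring rules follow. For pinprick: "Mechanical pain sensitivity will be calculated as the geometric mean of all numerical ratings for pinprick stimuli". For light touch: "Dynamic mechanical allodynia will be calculated as the geometric mean (compound measure) of all numerical ratings", taken over the three kinds of stimulator together. Light touch is assessed within the pinprick test, so the same scale applies. Neither rule adds a constant or says what happens to a rating of 0.

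The wind-up ratio, also from 0–100 ratings, is the "mean rating of the five series divided by the mean rating of the five single stimuli".

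Section 16 converts sensory-testing values to z-scores against a normal population. It describes up to 100 patients at two centres "providing QST data at baseline which can be used to identify a preferential profile for responders to the FREMS treatment". It also uses the tests to look for recovery or worsening of sensory function at 3 months.

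**The concern.** The formula does not work on the scale to which it is applied. A geometric mean is a product raised to a power, so a single zero factor removes the information in every other rating. Zero is a natural answer here. The protocol itself calls the light-touch stimuli innocuous, the pinprick set starts at 8 mN, and every participant has diabetic neuropathy.

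Followed exactly, the rule gives a participant with clear but not universal allodynia the same DMA as one with none. It also makes the score jump between visits when a single rating moves to or from 0. A responder profile or a gain-of-function z-score built on such values could miss a real difference or show a false one.

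**Working it through.** **Inputs (section 16.1).** Rating scale 0–100, with 0 allowed. Stimuli come in runs of 10, and "each run will consist of a different pseudo-random sequence of three tactile and seven pinprick stimuli".

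**Reproducing the stimulus count.** 50 / 10 = 5 runs. Tactile: 5 × 3 = 15. Pinprick: 5 × 7 = 35. Total 50, as stated. So n = 35 ratings enter MPS and n = 15 enter DMA.

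**Formula as written.** GM = (x₁ × x₂ × … × xₙ)^(1/n). If any xᵢ = 0, the product is 0 and GM = 0; on the log scale, log 0 is undefined.

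**Worked cases**

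| Ratings | As written | Arithmetic mean, for scale |
|---|---|---|
| DMA: fourteen of 20, one of 0 | 0 | 14 × 20 / 15 = 18.7 |
| DMA: fourteen of 30, one of 0 | 0 | 28.0 |
| MPS: thirty-four of 40, one of 0 | 0 | 38.9 |
| DMA: fifteen of 0 | 0 | 0 |

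The first two rows cannot be told apart from the last. The break is abrupt: fourteen ratings of 20 and one of 1 give 20^(14/15) = 16.4, but changing that 1 to 0 gives 0.

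**With a constant (illustration only).** Adding 0.1 to each rating in the first row gives (20.1¹⁴ × 0.1)^(1/15) = 14.1. The result depends on the constant. Ten ratings of 30 and five of 0, with c added before and subtracted after, give 4.4 (c = 0.1), 7.2 (c = 0.5) and 8.9 (c = 1).

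**How many participants?** The protocol gives no zero rate, so this part is an assumption. If each rating is 0 independently with probability p, P(score = 0) = 1 − (1 − p)ⁿ:

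| p | MPS (n = 35) | DMA (n = 15) |
|---|---|---|
| 1% | 30% | 14% |
| 5% | 83% | 54% |
| 10% | 97% | 79% |
| 20% | >99.9% | 96% |

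Independence is one extreme. At the other, a participant's ratings are either all zero or all non-zero. Then a share p scores 0, correctly, and nobody is mis-scored.

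**Wind-up ratio.** The denominator is a mean of five ratings, so it is 0 only if all five are 0. Under independence the probability is p⁵: about 0.00003% at p = 5%, 0.001% at 10%, 0.03% at 20% and 3.1% at 50%. One zero does no harm: five series ratings of 30 against single ratings of 10, 10, 10, 10 and 0 give 30 / 8 = 3.75.

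**Measures not affected.** The mechanical detection and mechanical pain thresholds (MDT, MPT) are also geometric means, but of applied forces, which start at 0.25 mN and 8 mN and are never 0. The thermal thresholds and the vibration threshold (VDT) do not use a geometric mean of ratings.

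**The case against.** The best defence is that section 16.1 only summarises a cited procedure. Sections 16 and 16.1 say testing follows the German Research Network protocol, and section 14.2 leaves analytic detail to a separate SAP. Either document may contain a rule for zeros, and a later rule would lose nothing if each of the 50 ratings is kept. It is right that a reader should not conclude that no such rule exists. But section 16.1 does more than leave a detail out: it writes the calculation in full, and that calculation fails on ratings its own scale permits. A general reference elsewhere does not alter the formula on the page.

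Three further objections stand and limit the point.

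- A reader might infer that the scores collapse for most participants. The documents do not support that. It needs an assumed zero rate and independent zeros, whereas zeros would plausibly cluster by person and by stimulus force. For someone who rates every light stroke 0, DMA = 0 is the right answer.
- A reader might infer that wind-up will be lost selectively in the least sensitive participants. That requires strong within-person clustering, and it cannot be argued alongside the independence behind the table. Under independence the loss is negligible.
- A reader might infer that the safety check on sensory function is undermined. MPS is described as a test for pinprick hyperalgesia, which is a gain. Sensory loss is covered by the thermal thresholds, MDT, MPT and VDT, none of which uses the faulty calculation.

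**Conclusion.** The point holds for MPS and DMA. As written, any participant with mixed zero and non-zero ratings receives a score of 0 (or an undefined one), identical to that of a participant with no evoked pain. This is algebra and rests on no assumption. The share of participants affected is unknown. The percentages above show only what independent zeros would imply, and clustering would lower them, to no mis-scoring at all in the extreme.

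The reach is limited: two scores in an exploratory sub-study of up to 100 patients at two centres, used for the responder profile and gain-of-function z-scores. The primary outcome, the sample size, the main analysis and the sensory-loss measures are unaffected. The wind-up ratio is a minor addition, undefined only when all five single-stimulus ratings are 0.

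**What to change.** In section 16.1, replace the two formulas. MPS and DMA should each be a geometric mean taken after a fixed small constant has been added to every rating. The constant and the handling of zeros, including whether the constant is subtracted afterwards, should be those of the reference protocol behind the normative values. Because section 16 turns these scores into z-scores, a constant that differs from the one behind the reference values could bias them; the 0.1 used above is illustrative and not a recommendation. Name the constant, cite its source and apply it identically at all visits.

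Add one sentence saying that the wind-up ratio is undefined when all five single-stimulus ratings are 0, and that the number of such cases is reported by arm.

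The cost is a wording change, with no new data and no change to the testing. Results will still depend somewhat on the constant, which is why it should be fixed in advance and matched to the reference values.

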17. TRIAL ORGANISATIONAL STRUCTURE

17.1 Sponsor

The Sponsor for this trial is University of Birmingham (UoB).

17.2 Coordinating centre

The trial coordinating centre (Trial Office) is Birmingham Clinical Trials Unit (BCTU), based at UoB.

17.3 Trial Management Group

The Trial Management Group (TMG) will take responsibility for the day-to-day management of the trial and will include (but is not limited to) the CI, co-lead, Trial Statistician, Trial Manager, Health Economist and senior BCTU oversight staff. The role of the group is to monitor all aspects of the conduct and progress of the trial, ensure that the protocol is adhered to and take appropriate action to safeguard participants and the quality of the trial itself. The TMG will meet sufficiently frequently to fulfil its function.

17.4 Co-investigator group

The Co-investigator group, an extended TMG, will comprise all members of the co-applicant group and the members of the TMG to review progress, troubleshoot and plan strategically.

17.5 Trial Steering Committee

A TSC will be established for the FREMS-PDPN trial. The TSC will include members who are independent of the investigators, their employing organisations, funders and sponsors. The TSC composition will be chaired by an independent member and will include an independent Statistician, clinicians, health economist and a patient representative.

The TSC will operate in accordance with a trial specific TSC Charter. Membership and duties/responsibilities will be outlined in the TSC Charter. In summary, the TSC will provide overall oversight of the trial including the practical aspects of the trial and ensure the trial is run in a way which is both safe for the participants and provides appropriate data to the sponsor and funder. The TSC will consider and act, as appropriate, upon the recommendations of the DMC.

The TSC will meet at the start of the trial, prior to recruitment of any patients and then will aim to meet at least annually thereafter by videoconference, at face-to-face meetings or via e-mail communication of updates of reports.

17.6 Data Monitoring Committee

The role of the independent DMC is to monitor the trial data, and make recommendations to the TSC on whether there are any ethical or safety reasons as to why the trial should not continue or whether it needs to be modified. To this end, data on safety outcomes and (where appropriate) primary and major secondary outcomes will be supplied to the DMC during the trial.

Data analyses will be supplied in confidence to a DMC, which will meet prior to trial commencement to agree the manner and timing of such analyses. The DMC will be asked to give advice on whether the accumulated data from the trial, together with the results from other relevant research, justifies the continuing recruitment of participants. The DMC will operate in accordance with a trial specific DMC Charter. The DMC will meet at least annually as agreed by the Committee and documented in the Charter.

Additional meetings may be called if recruitment is much faster than anticipated and the DMC may, at their discretion, request to meet more frequently or continue to meet following completion of recruitment. An emergency meeting may also be convened if a safety issue is identified. The DMC may consider recommending the discontinuation of the trial if any issues are identified which may compromise participant safety. The DMC may recommend early stopping of the trial if the interim analyses show differences between treatments that are deemed to be convincing to the clinical community. Further details on the trial stopping guidelines will be outlined in the DMC Charter and the Statistical Analysis Plan.

17.7 Finance

The research costs of the trial are funded by a NIHR Health Technology Assessment (HTA) grant, reference NIHR133599, awarded to [name] and UoB. The trial has been designed to minimise extra 'service support' costs for participating hospitals as far as possible. Additional costs, service support costs and excess treatment costs associated with the trial, e.g. gaining consent, are estimated in the Schedule of Events Cost Attribution Template. These costs should be met by accessing the Trust's Support for Science budget via the Local Comprehensive Research Network. Participants will be reimbursed up to £10 travel costs for each trial specific visit.

